### **7.5 Power Calculation**

Based on a published randomized placebo-controlled trial in patients with probable AD, oral NAC treatment resulted in a significant improvement in executive function in the active treatment group ( $p= 0.008$ ) but not in placebo. Our preliminary analysis of MOVE-IT blinded data ( $n=30$ ) was used to provide an updated estimate of the standard deviation ( $SD=0.55$ ) of executive function Z-scores in our population, controlling for education. Based on this, a sample size of 42 (21 in each group) will provide 80% power, at alpha of 0.05, to detect a medium effect size in a linear mixed model with a hypothesized intra-cluster correlation of 0.1. The sample size calculation was carried out using PASS Version 12 (Kaysville, Utah.). Due to the uncertainties of COVID-19 pandemic, a generous drop-out rate was used. To account for a drop-out rate of 42%, we will inflate the sample size to 60.

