## 5 PARTICIPANT SELECTION AND WITHDRAWAL

A total of 60 mild VCI patients will be recruited from the CR program at the University Health Network Toronto Rehabilitation Institute.

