
## 7.4 Statistical Analyses

All analyses will be performed using current versions of SPSS and SAS (SAS Institute, Cary, NC, USA). The intention-to-treat analyses will be based on data from all patients who undergo randomization, meet the inclusion criteria for the study, receive the trial medication at least once, and undergo at least baseline observation. Descriptive statistics will be calculated for composite z-scores for executive function, memory, and speed of processing. Categorical variables will be summarized using counts and percentages. Continuous variables will be compared between groups using two sample two sided t-tests (or Wilcoxon rank sum tests for non-normal data), whereas categorical variables will be compared between groups using chi-square analyses or Fisher's exact tests.

Primary Hypothesis: Differences in executive function composite z scores between the groups at 24 weeks will be compared between treatment groups using a two sample two sided t-test. A linear mixed model will be run to compare the rate of change in the executive function measure over time (baseline, 12- and 24-weeks). The linear mixed model is selected as it can accommodate missing data in subjects. The effects of age, sex, BMI, total years of education, VO2 peak, physical activity levels, serum homocysteine, will be included as possible covariates. The same analyses will be repeated with the composite z-scores of the other cognitive domains as repeated variables to test for the effect of NAC treatment on the secondary outcome measures.

Secondary Hypotheses: A linear mixed model will also be used to test the hypothesis that patients with mild VCI treated with NAC will show a greater reduction in 8-ISO/LPH ratio over 24 weeks of treatment. The early to late stage lipid peroxidation marker ratio will be inputted as the repeated variable, and treatment group will be added as a fixed factor. The effects of group by time interaction will be evaluated to indicate significant effects of NAC in reducing oxidative stress markers as compared to placebo. APOE4 genotype status, BMI, VO2 peak, and sex will be added as covariates. Similar analyses will be conducted separately with GPx, GR and GST inputted as the repeated variable. Logistic regression analyses will be performed to examine whether baseline severity of WMH is a significant predictor of cognitive response to NAC treatment at 24 weeks, adjusting for the same covariates.

Exploratory Hypothesis:

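### Sixty patients do not cover the stated 42% drop-out: about 35 would complete, not the required 42, and 60 allows for only 30%

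*Combined protocol and SAP*

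**What the plan says.** Section 7.5 (Power Calculation) sets the evaluable requirement first: "a sample size of 42 (21 in each group) will provide 80% power, at alpha of 0.05". The target is described as "to detect a medium effect size in a linear mixed model with a hypothesized intra-cluster correlation of 0.1". The section explains that the drop-out allowance was set high on purpose because of the COVID-19 pandemic, and concludes: "To account for a drop-out rate of 42%, we will inflate the sample size to 60".

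The figure of 60 is also the sample size in the Protocol Summary and the recruitment target in section 5 ("A total of 60 mild VCI patients will be recruited"). Section 7.5 is the only place where it is justified. Nowhere do the documents define the 42% as anything other than a drop-out rate in the ordinary sense, a proportion of the patients enrolled.

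**The concern.** To keep n evaluable patients when a proportion d of those enrolled is lost, the enrolled number must be n/(1 - d). Multiplying by (1 + d) is a familiar slip. It is nearly harmless when d is small, but at 42% the two forms are far apart. The stated 60 is what the multiplying form gives.

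The sentence tells the reader, the ethics board and the funder that the trial keeps its planned power with 42% of patients lost. If it does not, the only stated basis for the enrolled number is wrong, and wrong in the direction that overstates how much attrition the trial can bear.

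**Working it through.** **Inputs, all from section 7.5 unless noted**

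- Evaluable patients required, n = 42 (21 per group)
- Power 80%, alpha 0.05; two-sided, taken from section 7.4, where the 24-week scores "will be compared between treatment groups using a two sample two sided t-test"
- Drop-out rate d = 0.42
- Enrolment N = 60 (also in section 5 and the Protocol Summary)

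**Step 1. Reproduce the plan's figure**

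n x (1 + d) = 42 x 1.42 = 59.64, rounded up to 60. Per arm, 21 x 1.42 = 29.82, rounded up to 30, which again gives 60. The figure is reproduced by this form.

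**Step 2. Enrolment needed at 42% drop-out**

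n/(1 - d) = 42/0.58 = 72.4, so 73 patients. With equal arms, 21/0.58 = 36.2, so 37 per arm and 74 in total.

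**Step 3. Completers from 60 at 42% drop-out**

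N x (1 - d) = 60 x 0.58 = 34.8, about 35 (17.4 per group). The shortfall is 42 - 34.8 = 7.2 patients, and 7.2/42 = 17%.

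**Step 4. Drop-out that 60 can absorb**

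1 - 42/60 = 0.30, that is 30%.

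**Step 5. Is it rounding of the rate?**

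| Rate | n x (1 + d) | n/(1 - d) |
|---|---|---|
| 41% | 59.2, so 60 | 71.2, so 72 |
| 42% | 59.6, so 60 | 72.4, so 73 |
| 43% | 60.1 | 73.7, so 74 |

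No rate close to 42% makes 60 the right answer under the dividing form.

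**Step 6. Could 42% be a share of the 42?**

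The patients added are 60 - 42 = 18, and 18/42 = 42.9%. The figure therefore fits approximately as a share of the evaluable number, but that is not a drop-out rate among enrolled patients, and the text does not define it so.

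**Step 7. Effect on power**

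Take the plan's claim of 80% at 42 patients as given. For a two-sided 5% test under the normal approximation, the standardised effect at 42 is 1.960 + 0.842 = 2.80. It scales with the square root of the sample size:

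- 2.80 x sqrt(34.8/42) = 2.80 x 0.910 = 2.55
- Power = Phi(2.55 - 1.96) = Phi(0.59) = about 0.72

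The effect size, the SD of 0.55 and the intra-cluster correlation of 0.1 all cancel in this ratio, so the unspecified size of the medium effect does not matter here. The calculation counts complete cases only.

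**The case against.** Four points can be made for the plan.

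- **The cause is inferred.** Section 7.5 shows no working. Since 42/0.70 = 60 exactly, 60 is also the correct inflation for 30%, and the 42% could be a misprint that repeats the 42 given earlier in the section. This stands: the documents prove only that 42, 42% and 60 are inconsistent. On either reading the sentence is wrong.
- **The powered analysis is a mixed model.** Section 7.4 chose it partly because it tolerates missing data. Cognition is measured at 12 as well as 24 weeks, and section 5.4.2 asks withdrawing patients for a final visit. Patients who leave early can therefore still contribute, and 35 patients with 72% power is close to a worst case for that model. This stands as a limit on the consequence. It does not rescue the sentence: the inflation step itself treats drop-outs as lost, and the week-24 t-test, named first for the primary hypothesis, cannot use a patient without a week-24 value.
- **The shortfall is conditional.** It appears only if drop-out exceeds 30%. The plan calls its own rate generous, and nothing in the documents says that losses above 30% are expected. This also stands, but protection against a high loss is what the sentence claims.
- **Nothing in the conduct of the trial changes.** Eligibility, visits, endpoint and analysis are unaffected, and 60 remains the figure in section 5. This is true, and it is why the remedy is small. It is no reason to leave an incorrect figure as the basis of the sample size.

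**Conclusion.** The concern holds. The plan's three figures cannot all be true together, and 60 protects 42 completers only up to 30% drop-out.

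The inconsistency is certain and rests on the plan's own numbers, with drop-out read as a proportion of those enrolled. The multiplication by 1.42 is the likely explanation, not an established one. The fall in power to about 72% is an approximation. It assumes that 42 patients do give 80%, that drop-outs contribute nothing, and that the full 42% is lost.

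Whether 42 evaluable patients really provide 80% power is a separate question, on which this conclusion does not depend.

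**What to change.** Keep enrolment at 60 and correct the last sentence of section 7.5 in one of two ways:

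1. State that 60 patients allow for 30% drop-out while retaining 42 evaluable patients (42/0.70 = 60).
2. Keep the 42% assumption, state that it leaves about 35 completers from 60, and give the power for 35. On the scaling above this is about 72% for complete cases. If the mixed model is expected to recover part of the loss, the sponsor should give the power under a stated pattern of missing data.

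The sponsor has to say which drop-out rate it intends, since the documents do not settle whether the rate or the inflation is the mistake.

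The cost is one sentence. Section 5 and the Protocol Summary need no change. The price is candour: the stated drop-out tolerance, or the stated power, becomes less favourable than it now reads.

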### **Protocol Deviations**

Planned deviations from the protocol will not be implemented without prior agreement from the sponsor and approval from Sunnybrook Health Sciences Centre REB, unless to eliminate an immediate hazard to a participant. Protocol deviations will be documented and reported as required and assessed where necessary during statistical analysis.

## 8 ASSESSMENT OF SAFETY

The safety of research participants is foremost and should always be considered throughout the conduct of research.

### 8.1 Definitions

#### 8.1.1 *Adverse Events*

An adverse event (AE) means any untoward medical occurrence in a patient or clinical investigation participant administered a pharmaceutical product and which does not necessarily have to have a causal relationship with this treatment, and includes an adverse drug reaction (ADR).

An AE can therefore be any unfavorable and unintended sign (including an abnormal laboratory finding, for example), symptom, or disease temporally associated with the use of a medicinal product, whether or not considered related to the medicinal product.

#### 8.1.2 *Serious Adverse Events*

A serious adverse event (SAE) or reaction is any untoward occurrence that at any dose:

- Results in death,
- Is life-threatening,
- Requires inpatient hospitalization or prolongation of existing hospitalization,
- Results in persistent or in significant disability/incapacity,
- Is a congenital abnormality or a birth defect.

The term "life-threatening" in the definition of "serious" refers to an event in which the participant was at risk of death at the time of the event; it does not refer to an event which hypothetically might have caused death if it were more severe.

#### 8.1.3 *Unexpected Adverse Event*

An unexpected adverse event is any AE that is not identified in nature, severity or frequency in the current Product Monograph.

#### 8.1.4 *Unexpected Adverse Drug Reaction (ADR)*

An ADR is an adverse reaction, the severity of which is not consistent with the applicable Product Monograph. All noxious and unintended responses to a medicinal product related to any dose should be considered an ADR.

The phrase "responses to a medicinal product" means that a causal relationship between a medicinal product and an adverse event is at least a reasonable possibility, i.e., the relationship cannot be ruled out.

The expression "causal relationship" is meant to convey that in general there are facts, evidence or arguments to suggest a reasonable causal relationship. All serious and unexpected ADRs will have expedited reporting to regulatory agencies following ICH-GCP and local regulatory requirements.

## **8.2 Assessment of an Adverse Event**

### **8.2.1 *Relationship (Causality/Relatedness)***

The causality assessment is the determination, according to the investigator's clinical judgment, of the existence of a reasonable possibility that the study drug (IP) caused or contributed to an adverse event.

If the qualified investigator or delegated sub-investigator is unsure about whether or not the study drug caused or is related to the event, then the event will be handled as "related" to the study drug for reporting purposes of the trial. If the causality assessment is "unknown but not related" to the study drug, this will be clearly documented in the source documents.

### **8.2.2 *Expectedness***

Events will be classified as unforeseen or unexpected if the nature, severity or frequency is not consistent with the risk information set out in the Product Monograph or label.

### **8.2.3 *Seriousness***

Events will be classified as serious if associated with effects threatening the life or physiological functions of a participant. Refer to the definition for "Serious Adverse Events" in section 8.1.2.

### **8.2.4 *Severity***

The term "severe" is often used to describe the intensity (severity) of a specific event (e.g. mild, moderate, or severe myocardial infarction); the event itself, however, may be of relatively minor medical significance (such as severe headache). This is not the same as "serious," which is based on participant/event outcome or action criteria usually associated with events that pose a threat to a participant's life or functioning. The terms "serious" and "severe" are not synonymous. Seriousness (not severity) serves as a guide for defining regulatory reporting obligations.

## **8.3 Adverse Event Recording**

Investigations into potential adverse events will be conducted throughout the study (in person during the baseline visit, and at 4, 8, 12, 16, 20 and 24 weeks; and over the phone as shown on Appendix A) using a symptom checklist and will be recorded promptly in the source document. This checklist will include all potential side effects listed on the current product monograph for NAC. All emerging AEs will be noted and followed-up until resolution in a timely manner.

### **8.3.1 *Investigator reporting: Notifying the REB***

Serious adverse events and unanticipated events will be recorded and reported to the REB in accordance with local reporting requirements and timelines.

### **8.3.2 *Investigator reporting: Notifying the Sponsor***

The investigator will report serious adverse events and serious and unexpected adverse drug reactions (SUADRs) to the sponsor in accordance with applicable regulations and reporting requirements and timelines.

### ***8.3.3 Sponsor Reporting of SUADRs: Notifying Health Canada***

The regulatory sponsor will report SUADRs to regulatory authorities in accordance with local expedited reporting requirements and timelines. In addition, the Sponsor will complete the ADR Expedited Reporting Summary Form and submit this form in conjunction with the completed CIOMS Form to the appropriate Health Canada directorate..

### ***8.3.4 Sponsor Reporting of SUADRs: Notifying Sites***

The regulatory sponsor is responsible for distributing blinded expedited reports of SUADRs to each investigator for submission to local Ethics Committees within 15 days of sponsor awareness.

## **8.4 Type and Duration of Follow-up for Adverse Events**

AEs occurring as of the first administered dose of the investigational product and to a follow up period of at least 32 hours (half life of NAC is 6.25hrs) after the last administered dose, will be collected. AEs recorded during this period will be followed through to resolution, or until the event is assessed as chronic or stable.

## **8.5 Reporting and Entry Timelines**

The principal investigator will report SAEs to the sponsor within the following timelines:

- All deaths and immediately life-threatening events, whether related or unrelated, will be recorded and reported to the sponsor within 24 hours of site awareness.
- Serious adverse events other than death and immediately life-threatening events, regardless of relationship, will be reported to the sponsor within 72 hours of site awareness.

Adverse event information will be entered into the CRF in a timely manner and **no later than 15 days** from the time the investigator becomes aware of the event.

Serious adverse event information will be entered into the CRF in a timely manner/**within 72 hours** from the time the investigator becomes aware of the event.

## **8.6 Rescue Medication**

In case of overdose, the managements should be focused on the treatment of symptoms. These symptoms should be managed according to current standards of care with general supportive measures. Also discontinuation of study drug should be considered.

## **9 SITE MONITORING, AUDITING AND INSPECTING**

### **9.1 Site Monitoring Plan**

The extent and nature of monitoring is outlined in the Study Monitoring Plan. Monitoring activities will be performed both in person and remotely. Reports of findings identified during monitoring activities will be provided to sites detailing any required actions. Documentation of monitoring activities and findings will be provided to the site study team and the study QI. The institution and/or local REB reserves the right to conduct independent audits as necessary.

### **9.2 Auditing and Inspecting**

The investigator will provide direct access to source data/documents for the purposes of study-related monitoring, audits, and inspections by the REB, the sponsor, and applicable regulatory bodies. The investigator will permit the review of all study related documents (e.g. source documents, regulatory documents, data collection instruments, study data etc.) and will ensure access to applicable study-related facilities (e.g. pharmacy, diagnostic laboratory, etc.).

## 10 DATA HANDLING AND RECORD KEEPING

### 10.1 Confidentiality

Information about study participants will be kept confidential and managed according to the requirements of the Personal Health Information Protection Act of 2004 (PHIPA) and the Research Ethics Board. PHIPA outlines the rules for the collection, use and disclosure of personal health information.

### 10.2 Source Documents

The investigator(s) and research team members listed on the Task Delegation Log will have access to participant medical records and will collect only the information needed for the study. Sponsor delegated monitors, representatives of institutional committees and regulatory authority representatives will also have access to examine records for the purposes of quality assurance reviews, audits and evaluation of study safety and progress.

Data will be collected on printed source documents/case report forms (**CRFs**). Source documents/CRFs include physical, cognitive, and clinician assessments.

### 10.3 Data Management Responsibilities

As part of the safety plan for this study, the investigator will review individual study participant records to ensure that appropriate mechanisms to protect the safety of study participants are being followed, that protocol requirements are being adhered to, and that data is accurate, complete, and secure. Participant records include, but are not limited to: consent forms, case report forms, data forms, laboratory records, inclusion/exclusion forms, and medical charts. All study data will be collected by a member of the study research team and recorded in accordance with applicable procedures.

### 10.4 Data Capture

#### 10.4.1 Case Report Forms

The study case report form (CRF) is the primary data collection instrument for the study. Paper case report forms (pCRFs) will be used to collect data for this study. CRFs will be completed by data capture personnel and signed off by the investigator in a timely manner. Data from pCRFs will be electronically entered into Research Electronic Data Capture (REDCap). Good documentation practices will be implemented according to standard operating procedures. All data reported on the CRF will be verifiable by source document.

### 10.5 Records Retention

Study essential documents will be maintained in a secure and confidential manner for a period of 25 years. For the purposes of this study, the start date of the retention period will be the date of the final report of the trial. All study records will be destroyed according to local and national policy and requirements. The sponsor will inform the investigator/institution when these documents may be destroyed.

## **10.6 Clinical Trial Registration**

In accordance with Health Canada's Notice "Registration and Disclosure of Clinical Trial Information, November 30, 2007", the study will be registered on Clinicaltrials.gov ([www.clinicaltrials.gov](http://www.clinicaltrials.gov)).

## **11 ETHICS CONSIDERATIONS**

### **11.1 Ethical Standard**

This study will be conducted in accordance with the principles set forth in The Belmont Report: Ethical Principles and Guidelines for the Protection of Human Participants of Research, and codified in the Tri-Council Policy Statement and/or the ICH E6.

### **11.2 Research Ethics Board (REB)**

The protocol, informed consent form(s), recruitment materials, and all participant materials will be submitted to the REB for review and approval. Approval of both the protocol and the consent form will be obtained before any participant is enrolled. Any amendment to the protocol will be approved by the REB before the changes are implemented in the study, unless to eliminate an immediate hazard.

### **11.3 Consent**

A consent form describing in detail the study procedures and risks will be reviewed with and given to each participant. Consent forms will be REB-approved, and the participant will be required to read and review the document or have the document read to him or her. The investigator or designee will explain the research study to the participant and answer any questions that may arise. The participant will sign the informed consent form prior to any study-related assessments or procedures. Participants will be given the opportunity to discuss the study with their surrogates or think about it prior to agreeing to participate. They may withdraw consent at any time throughout the course of the study. A copy of the signed informed consent document will be given to participants for their records.

## 12 PANDEMIC CONTINGENCY PLAN

### 12.1 Alternative Methods for Consenting

In order to reduce risk to study participants and staff in pandemic situation (e.g COVID-19), alternative consenting methods such as videoconference or telephone consents is available to participants.

#### 12.1.1 *Consent obtained remotely by phone or video conference*

The research team will arrange a three-way call or video conference with the participant, an impartial witness, and if desired and feasible, additional participants requested by the participant (e.g., next of kin). Research staff will mail or email the participant a form ahead of time, explain the consent forms and answer any question during the call or video conference. The consent forms will be signed by the participant and a witness, and sent back to the research team via mail or email. Research team will have PI review and sign the consent form, provide the participant with a copy for their records. The process will be documented.

